### **Conflict of Interest Statement**

[name] and [name] declare to be ITI fellows and to be involved in activities in favor of the Institute Straumann.

[name] declares that Ariminum Odontologica, of which is co-owner, is receiving contributions to perform research from different implant and biomaterial companies.

All the other authors declare no conflicts of interest.

### **Acknowledgements**

Grant from ITI number 1049\_2014

## **Abstract**

**Aim:** to compare the survival and success rates of 4 mm implants used as distal support of a maxillary full-arch FDPs with standard (10 mm) implants placed in association with a bilateral sinus floor augmentation procedure.

**Material and Methods:** Two groups will be randomly prepared, the Short group and the Standard group. In the Short group, one 4 mm long and 4.1 mm in diameter implant (extra-short implant) will be installed in each side of the posterior region of the maxilla. In the Standard group, bilateral sinus floor elevations will be performed. After 4 months of healing, one 10 mm long and 4.1 mm in diameter implant (standard implant) will be installed into each augmented sinus. In the frontal region, four 10 mm long implants will be installed in both groups. Clinical assessments and x-rays will be taken at prosthesis delivering (6-8 weeks after implant installation), and after 6, 12, 18 and 24 months.

## Introduction

Anatomical limitations to implant insertion in fully edentulous arches are frequently encountered in the posterior regions of the jaws, due to the presence of the mandibular canal and of the maxillary sinus. In such situations, the installation of standard implants ( $\geq 10$  mm) could be impossible.

An alternative might be the use of the so-called “tilted implants” that might allow the use of standard implants. Vertical augmentation procedures or sinus floor elevation might allow the installation of standard implants as well. Another alternative is the use of short implants, as recommended in a consensus conference for the lower occurrence of complications of this treatment compared the use of longer dental implants installed in augmented sinus. Another consensus report concluded that the use of  $\leq 6$  mm long implants are a valid option to be used as alternative to augmentation procedures to reduce morbidity incidence.

A recent article reported a high survival rate (91.7%) after 10 years of loading of 6 mm long implants supporting single FDPs in the posterior regions of both jaws. Recently, 4 mm long implants with a standard diameter have been used for the restoration of the posterior edentulous mandible with favorable results. However, RCTs reporting the results from full-arch FDPs that included 4 mm long implants placed in the posterior regions of the maxilla have not been published yet.

Hence, the aim of the present study will be to compare the survival and success rates of 4 mm implants used as distal support of a maxillary full-arch FDPs with standard (10 mm) implants placed in association with a bilateral sinus floor augmentation procedure.

## **Material and methods**

The Declaration of Helsinki was followed, and the protocol was approved by the Ethical Committee Interaziendale Bologna-Imola (protocol #15052; 9 September 2015).

All procedures, timing, and complications will be systematically explicated to the included patients and signed informed consents will be collected. The Consort checklist will be followed for this report (<http://www.consort-statement.org/>). The study will be registered in the ClinicalTrials.gov with the following identifier: **xxxxxxx**.

### *Study population*

This study will be designed as an RCT study. Twenty patients have been planned to be included in the present RCT. Two parallel groups will be randomly arranged, the Short group that will include the 4 mm long implants, and Standard group that will include only 10 mm long implants installed 4 months after bilateral sinus floor elevation. Participants recruitment and all clinical procedures will be performed at the Department of Biomedical and Neuromotor Sciences, Dental Clinic, University of Bologna, RN, Italy.

The following inclusion criteria will be adopted:

- Edentulous maxilla
- Willing to receive a full arch fixed restoration in the maxilla.
- Latest extraction at least 8 weeks before implant insertion
- Sinus floor height included between 4 to 6 mm
- Bone width in the distal segments sufficient to allow the insertion of a 4 mm long implant of standard diameter.
- In the anterior maxilla (from first premolar to first premolar) bone width sufficient to allow the insertion of 10 mm long implants of standard diameter.

Minor horizontal augmentations with GBR procedures was allowed in the anterior maxilla.

Moreover, the opposing arch have to present one of the following conditions:

- natural dentition (at least 10 elements from 3.5 to 4.5)
- FPDs of at least 10 elements (from 3.5 to 4.5) supported by teeth or implants
- Implant supported or teeth supported overdentures
- Adequate partial removable prostheses.

*Exclusion criteria:*

Systemic exclusion criteria

- Presence of conditions requiring prophylactic use of antibiotics (e.g., history of rheumatic heart disease, bacterial endocarditis, cardiac valvular anomalies, prosthetic joint replacements).

- Major systemic diseases, or medical conditions requiring prolonged use of steroids, or alcoholism or chronically drug abuse.
- Current pregnancy or breastfeeding women
- Smokers > 10 cigarettes per day
- Physical handicaps that would interfere with the ability to perform adequate oral hygiene
- Immunocompromised patients including patients infected with HIV
- Conditions or circumstances, in the opinion of the investigator, which would prevent completion of study participation or interfere with analysis of study results, such as history of non-compliance, or unreliability.
- Patients with an ongoing or previous treatment with bisphosphonates (for at least 2 months for oral therapy or 6 months for IV injection)

*Local exclusion criteria*

- Local inflammation, including untreated periodontitis
- Pre-cancerous oral lesions
- History of local irradiation therapy
- Severe bruxism or clenching habits
- Patients with inadequate oral hygiene or unmotivated for adequate oral home care
- Previous GBR or GTR treatment at the implant site
- Total removable prosthesis in the lower arch

*Randomization and assignment concealment*

A statistician not involved in the study performed the randomization in blocks of four and the assignments will be sealed in coded and opaque envelopes.

*Masking Procedure:* The surgeon will be blinded about the assignment until the time of the surgery. The outcome assessor will be blinded about the protocol.

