#### *Surgical procedures in the Standard implant group*

Bilateral sinus floor elevations using a lateral access will be performed using Cerabone as filler material and Collprotect to cover the antrostomy. After 4 months of healing, one bone level implant, 10 mm long and 4.1 mm in diameter, will be installed into each augmented sinus. In the frontal region (included between the second premolars), four bone level implants, 10 mm long and 4.1 mm or 3.3 mm in diameter will be installed. A non-submerged healing will be allowed.

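### Blocks of four at a single centre, with arms obvious once treated, could let a recruiter deduce up to about one third of the 20 allocations in advance

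*Combined protocol and SAP*

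**What the plan says.** The points below come from Material and methods.

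- **Sequence and concealment** (*Randomization and assignment concealment*): a statistician from outside the study "performed the randomization in blocks of four and the assignments will be sealed in coded and opaque envelopes". Four is the only block size given. Stratification is not mentioned, and neither is withholding the block size from those who recruit.
- **Size and arms** (*Study population*): "Twenty patients have been planned to be included in the present RCT" and "Two parallel groups will be randomly arranged". The allocation ratio is not stated.
- **Setting** (*Study population*): "Participants recruitment and all clinical procedures will be performed at the Department of Biomedical and Neuromotor Sciences, Dental Clinic, University of Bologna".
- **Masking** (*Masking Procedure*): "The surgeon will be blinded about the assignment until the time of the surgery". The outcome assessor is also masked.
- **Treatments** (the two *Surgical procedures* sections): in the Standard group, "Bilateral sinus floor elevations using a lateral access will be performed using Cerabone as filler material", with implants following after 4 months. The Short group receives 4 mm tissue level posterior implants, and no sinus procedure is described.
- **Discretion at entry** (exclusion criteria): one criterion covers circumstances "in the opinion of the investigator, which would prevent completion of study participation". Others turn on oral hygiene, motivation and whether bone width is sufficient.

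The protocol does not say whether the recruiter and the surgeon are different people, or when an envelope is opened relative to enrolment of the next patient.

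**The concern.** An opaque envelope hides the card inside it. It does not stop someone working out the card from those already opened. With two patients per arm in each block of four, the next allocation is settled once one arm has its two patients, and the fourth patient in every block is always settled. The department that recruits also treats, so it can see earlier allocations once those patients have had surgery.

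Some entry criteria are matters of judgement and plausibly related to bone level and implant survival. A recruiter who knows the next arm could, knowingly or not, let that influence who is enrolled and when. The planned Mann-Whitney comparison has no baseline adjustment, and with 10 patients per arm a few steered enrolments could matter.

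**Working it through.** **Inputs.** From the protocol: 20 patients, two arms, blocks of four (20 / 4 = 5 complete blocks), one centre. Assumed: 1:1 allocation (2 + 2 per block), and a block size that is always four. The protocol gives no predictability figure to reproduce.

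**1. Certain allocations with full knowledge.** A 2 + 2 block has six equally likely orders.
- AABB and BBAA: the third and fourth patients are certain, so 2 each.
- The other four orders: only the fourth patient is certain, so 1 each.

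Mean per block = (2 × 2 + 4 × 1) / 6 = 4/3. The general formula for n per arm in a block, 2n/(n + 1), gives the same at n = 2. Over five blocks, 5 × 4/3 = 6.67 of 20 (33%). The number is 5 + Binomial(5, 1/3), so it runs from 5 to 10, and the probability of 6 or 7 is 0.329 + 0.329 = 0.66.

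**2. Best guess.** Always guessing the under-represented arm gives n + 2^(2n−1)/C(2n, n) − 1/2 correct guesses per block. At n = 2 this is 2 + 8/6 − 0.5 = 2.83 of 4, or 70.8% (14.2 of 20, against 10 by chance).

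**3. What timing does to it.**

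| Earlier allocations in the block not yet known at the next enrolment | Certain per block | Certain of 20 |
|---|---|---|
| None | 4/3 | 6.67 (33%) |
| The latest one | 1/3 | 1.67 (8%) |
| The last two | 0 | 0 |

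In the second row only the fourth patient can be deduced, and only when the first two were in the same arm (2 of 6 orders).

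**4. Illustration of consequences.** Assumptions: full knowledge; steering only when the next allocation is certain; a 0.5 SD shift in the steered patients' prognosis, which has no source in the documents; a patient-level t test, 10 against 10. The certain fraction of each arm averages 1/3.
- Shift in opposite directions for the two arms: bias = 1/3 × 0.5 + 1/3 × 0.5 = 0.33 SD. The simulated false-positive rate is about 10%.
- Shift for one arm only: bias = 1/3 × 0.5 = 0.17 SD. The simulated false-positive rate is about 6.5%.

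**5. Alternatives, with all earlier allocations known.**

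| Scheme | Certain of 20 | Best guess correct |
|---|---|---|
| Blocks of four | 6.7 | 71% |
| One permuted 10:10 list | 2 × 10/11 = 1.8 | (10 + 2^19/184,756 − 0.5)/20 = 62% |
| Undisclosed random blocks of 4 and 6 (simulated; observer knows the possible sizes) | about 1.2 | about 69% |

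**The case against.** The plan has real safeguards: an outside statistician, coded opaque sealed envelopes, a surgeon masked until surgery and a masked assessor. Most entry criteria are objective. Full exposure needs a recruiter who knows the block size and learns every earlier allocation before enrolling the next patient. Because the surgeon learns an allocation only at surgery, the next patient may already be enrolled by then. If just the latest allocation is unknown, certain allocations fall to 1.67 of 20, about the 1.8 that a single list gives with full knowledge.

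Much of this stands. It makes one third an upper figure and puts the supported range at 0 to 33%. It does not remove the point, because nothing in the protocol secures that delay or separates recruiter from surgeon, and neither envelopes nor surgeon masking prevents deduction from treated patients.

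A reader might infer that one third of allocations will be known, or that the trial has a 10% false-positive rate. The documents support neither. The first omits the knowledge conditions. The second needs a two-way shift of assumed size and a patient-level t test, whereas *Data analysis* plans a Mann-Whitney test at implant level; nothing has been computed for implant survival. Nor does the future tense about sealing show that envelopes are still unopened: tenses are mixed throughout and enrolment status is not given.

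**Conclusion.** The point holds as a risk that could be reduced at little cost. Up to about one third of allocations (expected 6.7 of 20, range 5 to 10) could be deduced in advance. That rests on 1:1 allocation, a constant block size of four, and a recruiter who knows that size and all earlier allocations in the block. It drops to about 1.7 of 20 with one allocation outstanding and to 0 with two. The protocol leaves the timing open, so no single value in that range can be called the trial's actual exposure, and nothing shows that selection bias occurred. The bias and error rates in the illustration show only what steering could do under stated assumptions.

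Blocks of four bring little in return here. With one centre, no strata and no interim analysis described, a single 10:10 list gives the same balance at 20 patients.

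**What to change.** 1. For all envelopes not yet opened, have the independent statistician replace the blocks of four with one permuted 10:10 list or with undisclosed, randomly varying block sizes. The single list lowers the best-guess rate more; mixed blocks of 4 and 6 leave slightly fewer certain allocations.
2. Keep the block scheme out of the protocol that the clinicians hold.
3. Record consent, confirmed eligibility and enrolment number in a dated log before the next envelope in sequence is opened.
4. If some envelopes have been opened, apply this to the remaining ones only, and report the block size and the enrolment log so that readers can judge the exposure.

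The cost is a regenerated list of 20 lines, resealed envelopes and a short log, with no extra patients or visits and no change to treatment. The downside is that the arms may be slightly unequal if recruitment stops before 20.

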#### *Implants and biomaterial used*

The implants will be offered by Institute Straumann AG, Basel, Switzerland)

A natural bovine bone grafting material (Cerabone granules 1-2 mm, Botiss biomaterial GmbH, Zossen, Germany) will be used for sinus floor elevation.

A porcine dermis collagen membrane (Collprotect membrane, Botiss biomaterial GmbH, Zossen, Germany) will be used to cover the antrostomy.

Bone fillers and collagen membranes are distributed by Institute Straumann AG, Basel, Switzerland.

#### *Surgical procedures in the Standard implant group*

Bilateral sinus floor elevations using a lateral access will be performed using Cerabone as filler material and Collprotect to cover the antrostomy. After 4 months of healing, one bone level implant, 10 mm long and 4.1 mm in diameter, will be installed into each augmented sinus. In the frontal region (included between the second premolars), four bone level implants, 10 mm long and 4.1 mm or 3.3 mm in diameter will be installed. A non-submerged healing will be allowed.

#### *Surgical procedures in the Short group*

In each side of the posterior region of the maxilla, one tissue level implant, 4 mm long and 4.1 mm in diameter, will be installed. In the frontal region, four bone level implants, 10 mm long and 4.1 mm or 3.3 mm in diameter will be installed

#### *Maintenance care of the patients*

Amoxicillin and clavulanic acid will be administrated per os before and for the following 6 days. As painkiller, Ibuprofen 600 mg *per os* will be suggested if needed.

#### *Prosthetic procedures*

During the healing, a temporary removable prosthesis will be provided to the patients.

Six weeks after implant installation, impressions will be taken and a fixed metal ceramic full-arch screw-retained prosthesis will be fabricated and delivered within a week.

#### *Clinical evaluation*

Bone quality according to Lekholm and Zarb (1985) will be subjectively evaluated and the insertion torque will be assessed using a ratchet device (Institute Straumann AG, Basel, Switzerland), and categorized as follows:  $0 \leq 15$ ,  $15 < x < 35$ , and  $\geq 35$  Ncm. Plaque Control record (O'Leary et al., 1972), Bleeding on Probing (Lang et al., 1986), and probing depths will be assessed around Short and Standard implants at prosthesis delivering and after 6, 12, 18, 24 months. The

highest probing depth will be recorded and categorized as follows: 1-3 mm, 4-5 mm,  $\geq 6$  mm.

PROMs were compiled by each patient regarding esthetics, function, and comfort satisfaction using a VAS scale.

### *Data analysis*

Mean values will be obtained from the double measurements made at the mesial and distal aspects of each implant. Mean values will be calculated between the distal and mesial measurements for each implant.

At the tissue level implants, the height of the polished neck (1.8 mm) will be subtracted to obtain the level of the coronal margin of the rough surface. The marginal bone levels reported in the present article will be related to the position of the coronal marginal rough surface. Marginal bone changes over time will be calculated and differences between groups will be evaluated at implant level using

the Mann-Whitney test included in the Statistics software SPSS (IBM Inc., Chicago, IL, USA) The level of significance will be set at  $\alpha=0.05$ .

The primary variable will be the change of marginal bone level between the baseline and 1 and 2 years of follow-up.

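### The primary bone-level test counts a patient's two study implants as independent, so its type I error rises above 5% as within-patient correlation increases

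*Combined protocol and SAP*

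**What the plan says.** The Study population section sets the size of the trial: "Twenty patients have been planned to be included in the present RCT", in two parallel groups. Under Randomization and assignment concealment: "A statistician not involved in the study performed the randomization in blocks of four".

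Both surgical sections give each patient two study implants, one on each side, in the same arm. In the Standard group a 10 mm implant "will be installed into each augmented sinus" after bilateral sinus elevation. In the Short group: "In each side of the posterior region of the maxilla, one tissue level implant", 4 mm long. All of a patient's implants then carry one restoration: "a fixed metal ceramic full-arch screw-retained prosthesis will be fabricated and delivered within a week" (Prosthetic procedures).

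The Data analysis section averages the duplicate readings and then the two sites of an implant: "Mean values will be calculated between the distal and mesial measurements for each implant". Averaging stops there. The group comparison follows: "Marginal bone changes over time will be calculated and differences between groups will be evaluated at implant level using" the Mann-Whitney test in SPSS, with alpha at 0.05. The same section names marginal bone change to 1 and 2 years as the primary variable, and the Outcomes section lists the 2-year change as a primary outcome. The plan specifies no patient-level summary, mixed model, GEE or clustered rank test.

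**The concern.** The unit of randomisation is the patient and the unit of analysis is the implant. The Mann-Whitney null distribution treats the 40 implants as 40 independent values. The two implants of one patient share the host, the prosthesis, the opposing arch, oral hygiene and smoking status, so some positive correlation is to be expected. The test statistic then varies more under the null than the test allows for, and the test rejects too often.

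This is the only inferential test the plan specifies, and it bears on a primary outcome. If its level is not 5%, a p-value slightly below 0.05 cannot be relied on, whichever group it favours.

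**Working it through.** **Inputs from the document.** 20 patients (Study population); blocks of four (Randomization and assignment concealment); m = 2 study implants per patient (both surgical sections); Mann-Whitney at implant level with alpha 0.05 (Data analysis).

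**Assumptions, because the document is silent.** 1:1 allocation, so 20 patients form 5 full blocks and give 10 patients (20 implants) per arm; two-sided test; no lost patients or implants; ICC anywhere from 0 to 1.

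**Step 1: reproduce the stated 5%.** With 20 v 20 independent implants, U has mean 20 × 20 / 2 = 200 and standard deviation √(20 × 20 × 41 / 12) = 36.97. The two-sided cut-off is 200 − 1.96 × 36.97 = 127.5, so the test rejects at U ≤ 127. The exact null distribution gives this a level of 4.91%. The stated level therefore holds if the implants are independent.

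**Step 2: add within-patient correlation.** With m = 2 the variance is inflated by about 1 + (m − 1) × ICC = 1 + ICC. The large-sample level becomes

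2 × [1 − Φ(1.96 / √(1 + ICC))].

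At an ICC of 0.5: 1.96 / √1.5 = 1.600, which gives 11.0%. The effective number of implants per arm is 20 / (1 + ICC), here 13.3.

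**Step 3: check by simulation.** 400,000 trials per ICC, 10 patients per arm with two implants each, normal patient effect with variance ICC, implant error with variance 1 − ICC, no group difference.

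| ICC | Formula | Simulated, implant level | Effective implants per arm |
|---|---|---|---|
| 0 | 5.0% | 4.9% | 20.0 |
| 0.01 | 5.1% | 5.0% | 19.8 |
| 0.02 | 5.2% | 5.1% | 19.6 |
| 0.1 | 6.2% | 6.0% | 18.2 |
| 0.2 | 7.4% | 7.2% | 16.7 |
| 0.3 | 8.6% | 8.4% | 15.4 |
| 0.5 | 11.0% | 10.9% | 13.3 |
| 0.7 | 13.3% | 13.2% | 11.8 |
| 0.8 | 14.4% | 14.5% | 11.1 |
| 1 | 16.6% | 16.6% | 10.0 |

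Repeat simulations agree to within about 0.2 percentage points.

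**Step 4: vary the assumptions.** Implant-level type I error at ICC 0.2, 0.5 and 0.8:

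- one-sided test at 0.05: 6.7%, 9.0%, 11.3%
- 8 v 12 patients: 7.5%, 11.0%, 14.8%
- skewed (exponential) data: 7.8%, 10.8%, 13.7%
- 10% of implants lost at random: 6.8%, 10.3%, 13.5%

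With 8 patients per arm it is 8.0%, 10.5% and 12.9% at ICC 0.3, 0.5 and 0.7.

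**Step 5: one value per patient.** The exact Mann-Whitney test on 10 v 10 patient means rejects at U ≤ 23 and has a level of 4.33%. Simulated levels are 4.3% to 4.4% at every ICC. The exact version matters: the normal approximation without continuity correction rejects at U ≤ 24, a level of 5.24%.

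**The case against.** The main counter-argument is that the size of the problem is unknown. The documents give no ICC, and it may be low, because reading error enters a change score twice. The test is also slightly conservative under independence (4.91%), so at an ICC of about 0.01 or less the level does not exceed 5%. Both points stand. They limit how large the excess is known to be, but they do not justify the analysis: from an ICC of about 0.02 the level passes 5% and keeps rising, and nothing in the plan shows that the correlation is that small.

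A second objection is that a patient-level test does not secure the trial's overall error rate, since bone change is assessed at 1 and 2 years and implant survival is a further primary outcome. That is right, but it is a separate matter. The claim here concerns the level of each individual test.

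Third, averaging is not the only remedy; a method that accounts for clustering would also serve. That stands too. Averaging is preferred because it keeps the planned test and is exact at this sample size.

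Fourth, using the surviving implant's value when its pair is lost is safe only if loss is unrelated to bone change. Under random loss the patient-level test stayed at 4.0% to 4.6% (6,000 runs, so approximate). When the implants with most bone loss were the ones lost, 20% v 5% by arm, one check gave it a level of 7% to 10%. Another check under informative loss gave 10% to 13%, against 17% to 23% for the implant-level test. The rule is therefore a workable default that does better than the planned test, but it does not protect against informative loss.

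**Conclusion.** The concern holds. The plan states an analysis unit that does not match its randomisation unit, and the nominal 5% is not the level of the test once the within-patient correlation is more than negligible. Assuming 10 v 10 patients, a two-sided test and complete data, the excess is about 1 percentage point at an ICC of 0.1. The error rate roughly doubles at 0.5, and about 17% is the upper end. The mismatch and the direction of the error are certain; the size depends on a correlation the documents do not supply. Because this is the plan's only specified test and concerns a primary outcome, it should be corrected before the data are analysed.

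**What to change.** In the Data analysis section, replace the implant-level comparison with text along these lines:

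> Groups will be compared at patient level. For each patient, the mean bone-level change of the two posterior study implants will be calculated. If one of them is lost, the remaining implant's value will be used and the loss counted under survival. If both are lost, the patient has no bone-level value and both losses are counted under survival. The groups will be compared with an exact Mann-Whitney test on one value per patient.

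This should be the single primary method for bone change. A mixed model with a random patient effect may be added as a sensitivity analysis, using small-sample degrees of freedom: a normal reference where 18 degrees of freedom apply would itself give P(|t₁₈| > 1.96) = 6.6%. It is not an equivalent test, because it compares means under distributional assumptions. A brief justification of the lost-implant rule should accompany the text.

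The cost is a few sentences and no new data. P-values will generally be less favourable, because the comparison rests on 20 patients and not on 40 implants. For an illustrative shift of 0.8 SD, power is 62% at patient level against 67% at implant level if the ICC is 0, and 45% against 65% if it is 0.5. In the second case part of the apparent advantage comes from the inflated error rate.

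### The implant-level Mann-Whitney test ignores both the patient and the blocks of four: too liberal as planned if a patient's implants are correlated, and short of power under recruitment drift once moved to patient level

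*Combined protocol and SAP*

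**What the plan says.** - **Allocation.** Under Randomization and assignment concealment: "A statistician not involved in the study performed the randomization in blocks of four". No stratification factor is named.
- **Size and arms.** Under Study population: "Twenty patients have been planned to be included in the present RCT" and "Two parallel groups will be randomly arranged". The allocation ratio is not stated.
- **Study implants.** Short group: "In each side of the posterior region of the maxilla, one tissue level implant". Standard group: one 10 mm implant "will be installed into each augmented sinus". Either way there are two study implants per patient, 40 in all.
- **Test.** Under Data analysis, after the mesial and distal readings are averaged for each implant, "differences between groups will be evaluated at implant level using" "the Mann-Whitney test included in the Statistics software SPSS", at a level of 0.05. Patient, block and recruitment time are not mentioned.
- **Not given.** Effect size, SD, power, correlation between a patient's two implants, and any expectation about change over recruitment.

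**The concern.** The reference distribution of a test should match how treatment was assigned. Here it departs from the assignment in two ways, and the two act in opposite directions.

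First, patients were randomised, not implants. Ranking 40 implants as independent overstates the information if a patient's two implants resemble each other, and a false positive becomes more likely than 5%.

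Second, blocks of four keep the arms balanced through recruitment, so a trend shared by both arms (case mix, general surgical routine) largely cancels from the comparison. An unblocked rank test still counts that trend as noise. Its level falls below 5% and power is lost. All procedures take place at one clinic and only 20 patients are planned, so there is little power to spare. Correcting only the first fault would leave a patient-level test fully exposed to the second.

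**Working it through.** **Inputs from the plan.** 20 patients, blocks of four, two study implants per patient, Mann-Whitney, level 0.05.

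**Assumptions.** 1:1 allocation, two-sided test, normal errors, no dropout, true effect of 1 implant-level SD, ICC from 0 to 0.7. Drift is 0 to 3 implant-level SD in total from first to last patient, common to both arms, either linear or one mid-trial step. The plan has no power calculation to reproduce.

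**1. Mismatch in the reference set.** 20/4 = 5 blocks. Blocked allocation permits C(4,2)^5 = 6^5 = 7,776 assignments. Unrestricted 10:10 allocation, which a patient-level Mann-Whitney test assumes, has C(20,10) = 184,756. Only 7,776/184,756 = 4.2% of those could have occurred.

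**2. Ignored patient, no drift.** With two implants per patient the variance of the group contrast is inflated by 1 + ICC, so the level is about 2[1 − Φ(1.96/√(1 + ICC))]:
- ICC 0.3: 1.96/1.140 = 1.72, level 8.6%
- ICC 0.5: 1.96/1.225 = 1.60, level 11.0%
- ICC 0.7: 1.96/1.304 = 1.50, level 13.3%

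Simulation of the planned test (6,000 trials per cell, asymptotic p-value) agrees and adds linear drift:

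| ICC | no drift | 1 SD | 2 SD | 3 SD |
|---|---|---|---|---|
| 0 | 4.5% | 4.2% | 2.4% | 0.8% |
| 0.3 | 7.7% | 6.8% | 4.6% | 2.4% |
| 0.5 | 11.1% | 10.2% | 6.0% | 2.8% |
| 0.7 | 13.5% | 11.6% | 8.0% | 4.7% |

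Drift only offsets the clustering error. Blocking alone does not cure it: a van Elteren test on implants within blocks still rejects 7.3%, 9.8% and 12.5% of the time at ICC 0.3, 0.5 and 0.7 with no drift.

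**3. Ignored blocks, one value per patient.** At ICC 0.5 the variance of a patient mean is (1 + 0.5)/2 = 0.75. A linear drift of D over 20 equally spaced patients has variance of about 0.092D². An unblocked test counts this as noise although blocking removes nearly all of it from the contrast, so its level is about 2[1 − Φ(1.96√(1 + 0.092D²/0.75))]:
- D = 1: √1.123 = 1.060, level 3.8% (simulated 3.9%)
- D = 2: √1.491 = 1.221, level 1.7% (simulated 1.7%)

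**4. Power on patient means, ICC 0.5.** The aligned-rank test subtracts the block mean, ranks all 20 values and takes the exact p-value over the 7,776 allocations (3,000 trials per cell).

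| Drift in both arms | Mann-Whitney | Aligned rank | Difference (points) |
|---|---|---|---|
| none | 62.9% | 62.6% | −0.3 |
| 1 SD, linear | 59.6% | 64.9% | 5.3 |
| 1 SD, step | 50.1% | 59.7% | 9.6 |
| 2 SD, linear | 43.6% | 62.5% | 18.9 |
| 2 SD, step | 22.5% | 51.5% | 29.0 |
| 3 SD, linear | 26.0% | 61.4% | 35.4 |

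Over ICC 0.3 to 0.7 the difference is about 5 to 12 points at 1 SD and 16 to 31 at 2 SD, counting both shapes. The aligned-rank level stays between 3.8% and 5.3% over the same ICC range. It loses power under a step because a step after patient 10 falls inside the third block (patients 9 to 12).

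**5. Drift in one arm only.** With an effect of 1.2 SD and linear drift in the Short arm alone (both in SDs of the patient mean), power is 65% for Mann-Whitney and 67% for aligned rank at 1 SD, and 57% and 61% at 2 SD. Across the runs of this scenario the gain was about 2 to 6 points.

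**6. Choice of block-based test.** With no drift, exact van Elteren on patient means loses about 21 to 23 points against the patient-level Mann-Whitney test. Its attainable two-sided level is only 2.1%, and the next step up is 5.4%. The asymptotic version loses about 4 to 5 points, the aligned-rank test about 1 or less.

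**The case against.** The best case for leaving the blocks out is this. At patient level, ignoring them neither biases the comparison nor inflates type I error, so only efficiency is at issue, and the gain depends wholly on a trend that the plan does not describe. Learning specific to the 4 mm implant would arise in the Short group only, where blocking recovers just 2 to 6 points. Variation in film reading is already limited, since the outcome is a change from each implant's own baseline, read twice by one operator and calibrated on implant length. The aligned-rank test is also not the standard SPSS procedure.

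All of that stands, and it limits the weight of the block part. It does not answer the clustering part, which concerns validity and needs no drift.

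A reader might infer from the mismatch with the blocks that any drift makes the planned test conservative. The plan does not support that, because the test is run on implants: with correlated implants it is too liberal at no or moderate drift, and falls below 5% only at about 2 SD (ICC 0.3) or 3 SD (ICC 0.5 to 0.7). A reader might also take 20 points as the most that can be lost. It is roughly the figure for one assumed scenario, 2 SD of linear drift in both arms. The loss is about 5 points at 1 SD and exceeds 30 at 3 SD.

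**Conclusion.** The point holds in two parts of unequal weight. The larger is the unit of analysis: unless a patient's two implants are close to independent, the planned test does not hold its 5% level when drift is small or absent. The smaller is the block structure, which matters once the unit is corrected and then only if outcomes drift in both arms by something like 1 SD or more. The documents establish the mismatch itself. They do not establish that drift will occur or how large it would be, and every power figure here rests on assumed effect, ICC and drift. Nor is every block-based analysis free of cost: the near-zero cost without drift belongs to the aligned-rank test, not to van Elteren. The change is worth making because one short revision deals with both parts.

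**What to change.** In the Data analysis section:

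1. Define one value per patient, the mean change over the two study implants, and state how a patient with only one readable study implant enters.
2. Specify the aligned-rank test: subtract the block mean, rank all patients together, and take the p-value from re-randomisation within the blocks. With 7,776 allocations the smallest two-sided p-value is 2/7,776 = 0.0003, so the test is fine enough. Obtain the interval for the shift by inverting the same test.
3. State that the allocation ratio within blocks is 1:1, if it is, and that the statistician who made the list supplies block numbers after data lock.
4. Keep the Mann-Whitney test on patient values as a sensitivity analysis, and do not substitute exact van Elteren.

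The cost is SAP wording, block numbers that already exist, and a short script outside SPSS. No further patients or data are needed. Blocks with missing patients contribute less, but this loss is small. With 2 of 20 patients missing at random and an effect of 1.2 SD of the patient mean, power for Mann-Whitney and aligned rank was 61% and 60% with no drift, 55% and 60% at 1 SD total drift, and 41% and 61% at 2 SD.
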